5.3 LIFESTYLE CONSIDERATIONS

Lifestyle and diet therapy provided before the time of screening is to be continued during the study. Dietary and lifestyle counseling will be given by a healthcare professional on the day of randomization and as needed during the study, which should be consistent with international or local guidelines for participants with T2DM (with regard to the distribution of calories among carbohydrates, proteins, and fats, exercise, etc.).

Compliance with the diet and lifestyle counseling will be assessed in case of insufficient glucose control.

5.4 SCREEN FAILURES

Screen failures are defined as participants who consent to participate in the clinical study but are not subsequently randomized. A minimal set of screen failure information is required to ensure transparent reporting of screen failure participants to meet the Consolidated Standards of

Reporting Trials (CONSORT) publishing requirements and to respond to queries from regulatory authorities. Minimal information includes demography, screen failure reasons, eligibility criteria, and any serious adverse event (SAE).

A participant should not be randomized more than once. In cases where original screen failure was due to reasons expected to change during rescreening and based upon the Investigator's clinical judgment, the participant can be rescreened one time for this study.

5.5 CRITERIA FOR TEMPORARILY DELAYING ENROLLMENT/RANDOMIZATION/ADMINISTRATION OF STUDY INTERVENTION ADMINISTRATION

During a regional or national emergency declared by a governmental agency, if the site is unable to adequately follow protocol mandated procedures, contingency measures are proposed in Appendix 6 ([Section 10.6](#): Contingency measures for a regional or national emergency that is declared by a governmental agency) should be considered for screening/enrollment/randomization/administration of study intervention.

6 STUDY INTERVENTION(S) AND CONCOMITANT THERAPY

Study intervention is defined as any investigational intervention(s), marketed product(s), placebo, or medical device(s) intended to be administered to a study participant according to the study protocol.

6.1 STUDY INTERVENTION(S) ADMINISTERED

Table 3 - Overview of study interventions administered

| Intervention label | Intervention label 1 | Intervention label 2 | Non-Interventional |
|--------------------------------|--|--|--|
| Intervention name | iGlarLixi | IDegAsp | Metformin ± SGLT-2 inhibitor |
| Type | Drug | Drug | Drug |
| Dose formulation | Pen injector | Pen injector | Tablet |
| Unit dose strength(s) | 2 types of SoloStar pens with 2 different ratios of 1:1 or 2:1 (100 U/mL insulin glargine with 100 or 50 µg/mL lixisenatide). Each pen injector contains 3 ml of iGlarLixi solution. | Ryzodeg 70/30 FlexTouch® which contains 3 ml of 100 U/ml of insulin Degludec and insulin Aspart with a ratio of 70:30. | |
| Dosage level(s) | 
Dosing time: Once daily in the hour (0 to 60 minutes) before the first meal.
 
Starting dose: Initiated with the 1:1 Pen at a dose of 5-10 dose steps (5-10 U insulin glargine / 5 -10 µg lixisenatide) per Investigator's judgment.
 
Dose modification: Once a week titration according to the algorithm described in Section 6.1.4
 | 
Dosing time: Once daily before the largest meal. Time determined at the discretion of participants and Investigators at randomization and to remain unchanged during the treatment
 
Starting dose: 5-10 U per Investigator's judgment.
 
Dose modification: Once a week titration according to investigator's discretion, or refer to the algorithm described in Section 6.1.4
 | 
Metformin ± SGLT-2 inhibitor will be administered orally according to the locally approved label.
 
Daily dose of metformin ± SGLT2 inhibitor (if previously taken) will be continued and maintained at the stable dose until the end of the treatment unless there is a specific safety issue related to this treatment.
 
An SU, a glinide, an alpha-GI, or a DPP-4 inhibitor, if previously taken, will be stopped prior to randomization.
 |
| Route of administration | Self- administration via SC injection | Self-administration via SC injection | Oral administration |
| Use | Experimental | Active comparator | Background intervention |
| IMP or NIMP | IMP | IMP | NIMP |

| | | |
|-------------------------------|---|---|
| Packaging and labeling | Study Intervention will be provided in kit. Each kit will be labeled as required per country requirement. | Study Intervention will be provided in kit. Each kit will be labeled as required per country requirement. |
|-------------------------------|---|---|

Table 4 - Arms and associated interventions

| Arm name | 1 | 2 |
|---|-----------|---------|
| Associated interventions (intervention label[s]) | iGlarLixi | IDegAsp |

6.1.1 Devices:

Injectors:

iGlarLixi will be self-administered with a pen-injector.

There will be 2 pen-injectors with different insulin glargine/lixisenatide fixed ratios which allow insulin glargine titration from 5 U/day to 40 U/day while limiting lixisenatide dose to a maximum of 20 µg/day:

- 1:1 Pen: pen-injector with 3 mL of a sterile aqueous solution of 100 U/mL insulin glargine and 100 µg/mL lixisenatide (1 unit of insulin glargine per 1 µg lixisenatide). This pen-injector is to be used for the iGlarLixi treatment initiation and administration of daily iGlarLixi doses between 5 and 20 dose steps (5 U insulin glargine / 5 µg lixisenatide- 20 U insulin glargine / 20 µg lixisenatide) in increments of 1 dose step
- 2:1 Pen: pen-injector with 3 mL of a sterile aqueous solution of 100 U/mL insulin glargine and 50 µg/mL lixisenatide (2 units of insulin glargine per 1 µg lixisenatide). This pen-injector is to be used for administration of daily iGlarLixi doses between 21 and 40 dose steps (21 U insulin glargine / 10.5 µg lixisenatide and 40 U insulin glargine / 20 µg lixisenatide) in increments of 1 dose steps.

iGlarLixi pen-injectors will be provided to participants randomized to the iGlarLixi group at randomization visit and thereafter.

IDegAsp (Insulin Degludec and Insulin Aspart Injection) will be supplied as a sterile aqueous solution in a Ryzodeg 70/30 FlexTouch. IDegAsp pen must not be mixed with other insulins nor diluted.

The IDegAsp pen contains 3 mL of a sterile aqueous solution of 100 U/mL insulin Degludec and insulin Aspart with a ratio of 70:30.

All device deficiencies (including malfunction, use error and inadequate labelling) shall be detected, documented, and reported by the Investigator throughout the clinical investigation (see [Section 8.3.8](#)) and appropriately managed by the Sponsor.

6.1.2 Training for injection devices

Handling procedures of the pen-injectors administration technique will be provided in specific instructional pen-injectors leaflets. The participants will be trained on how to use the relevant pen injectors and needles correctly, how to store it, and how to change the needle by the study staff and provided with an instruction leaflet at randomization visit (V2, Day 1), for the pen-injector devices listed below.

At V2, depending on the randomized treatment group, participants will be trained on:

- 1:1 pen injector and 2:1 pen injector for participants randomized to receive iGlarLixi
- Ryzodeg 70/30 FlexTouch® for participants randomized to receive IDegAsp

Training will be repeated as often as deemed necessary by study site staff during the treatment period. Additional training is needed if participants need to switch from 1:1 Pen to 2:1 Pen. The pen-injectors and leaflet that the participant will need to use during the treatment period will be dispensed according to the visit. Each participant is supplied with the appropriate number of pen-injectors according to the dispensing scheme indicated in the study flowchart.

Pen-injectors should never be shared with others, even if the needle is changed. Participants must always use a new needle for each injection to help ensure sterility and prevent blocked needles.

Reuse or share needles with another person is not allowed. Participants must remove needles from pen-injectors after each injection completion.

Pen device-related issues (malfunctions) must be reported to the Sponsor via the procedure for product technical complaint (PTC), using the respective PTC form, which is described in a separate manual. See [Section 8.3.8](#) for guidelines for reporting PTC."

6.1.3 Dosage schedule

Injection time

iGlarLixi

iGlarLixi will be self-administered once daily in the morning in the hour (0 to 60 minutes) before the first meal using the pen-injector.

IDegAsp:

IDegAsp will be self-administered once daily before the largest meal of the day using Ryzodeg 70/30 FlexTouch® pen. The injection time will be determined at the discretion of participants and Investigators on the day of randomization and should remain about the same until the end of the treatment period.

Injection site

The study intervention should be administered by deep SC injection, alternating between the left and right anterolateral and left and right posterolateral abdominal wall or thighs or upper arms. Within a given area, location should be changed (rotated) at each time to prevent injection site skin reactions.

6.1.4 Starting dose and dose modification

6.1.4.1 iGlarLixi

Starting dose:

iGlarLixi is to be initiated with the 1:1 Pen. The recommended starting daily dose is 5 dose steps (5 U insulin glargine / 5 µg lixisenatide). A higher starting daily dose up to 10 dose steps (10 U insulin glargine / 10 µg lixisenatide) may be allowed in some cases according to the investigator's clinical judgment that a higher starting dose of iGlarLixi is considered necessary.

A starting daily dose greater than 10 dose steps (10 U insulin glargine / 10 µg lixisenatide) is not allowed, in order not to exceed the recommended starting dose of lixisenatide which is 10 µg.

Dose adjustment:

- After the first week, doses will be titrated once a week according to the dose adjustment algorithm described in [Table 5](#) to achieve glycemic target of fasting SMPG ≥ 80 and ≤ 100 mg/dL (≥ 4.4 and ≤ 5.6 mmol/L) while avoiding hypoglycemia.
- Thereafter, until the end of the treatment period, the dose will be adjusted as necessary to maintain this fasting SMPG target. A total daily dose greater than 40 dose steps (40 U insulin glargine / 20 µg lixisenatide) is not allowed. Doses may be modified at any time for hypoglycemia.

Dose modification will be based on a median of fasting SMPG values from the last 3 measurements, which may include the value measured on the day of titration, measured by the participant using glucometers and accessories supplied by the Sponsor for this study.

Table 5 - Dose adjustment algorithm for iGlarLixi

| Median of fasting SMPG values from the last 3 measurements, which may include the value measured on the day of titration | iGlarLixi dose adjustments (dose step/day) |
|---|--|
| >140 mg/dL (>7.8 mmol/L) | + 4 |
| >100 and ≤ 140 mg/dL (>5.6 and ≤ 7.8 mmol/L) | + 2 |
| Glycemic target: ≥ 80 and ≤ 100 mg/dL (≥ 4.4 and ≤ 5.6 mmol/L) | No change |
| ≥ 60 and <80 mg/dL (≥ 3.3 and <4.4 mmol/L) | - 2 |
| <60 mg/dL (<3.3 mmol/L) or occurrence of 2 (or more) symptomatic hypoglycemic episodes or one severe hypoglycemic episode (requiring assistance) documented in the preceding week | - 2 to -4 or at the discretion of the Investigator or medically qualified designee |

Median refers to intermediate SMPG value (the value between the lowest and the highest SMPG values when the values are ranked in a growing order).

Note: Choice of pen-injector for iGlarLixi:

- If the participant needs a total daily iGlarLixi dose of 5 to 20 dose steps, use the 1:1 Pen (100 U/mL insulin glargine with 100 µg/mL lixisenatide).

- If the participant needs a total daily iGlarLixi dose of 21 to 40 dose steps, use the 2:1 Pen (100 U/mL insulin glargine with 50 µg/mL lixisenatide).

Daily doses of iGlarLixi higher than 40 dose steps (40 U insulin glargine / 20 µg lixisenatide) must not be administered. In case a dose >40 dose steps iGlarLixi is needed to maintain HbA1c below predefined threshold value for rescue, the dose must be kept at 40 dose steps and a rescue therapy should be introduced (see [Section 6.8.4](#) for rescue therapy).

6.1.4.2 IDegAsp:

Starting dose:

The recommended starting daily dose is 5 U. A higher starting daily dose up to 10 U may be allowed in some cases if according to clinical judgment the investigator believes that a higher starting dose might be necessary. A starting daily dose greater than 10 U is not allowed.

Dose modification:

After the first week, dose will be adjusted weekly to reach and maintain glycemic target of fasting SMPG ≥ 80 and ≤ 100 mg/dL (≥ 4.4 and ≤ 5.6 mmol/L) while avoiding hypoglycemia. Titration should be based on median of fasting SMPG of 3 consecutive days measurements. According to their best clinical judgement, investigators can either follow the algorithm they usually use in their daily medical practice or the recommended algorithm below which is similar as used for iGlarlix

Table 6 - Dose adjustment algorithm for IDegAsp

| Median of fasting SMPG values from the last 3 measurements, which may include the value measured on the day of titration | IDegAsp dose adjustments (U/day) |
|---|--|
| >140 mg/dL (>7.8 mmol/L) | + 4 |
| >100 and ≤ 140 mg/dL (>5.6 and ≤ 7.8 mmol/L) | + 2 |
| Glycemic target: ≥ 80 and ≤ 100 mg/dL (≥ 4.4 and ≤ 5.6 mmol/L) | No change |
| ≥ 60 and <80 mg/dL (≥ 3.3 and <4.4 mmol/L) | - 2 |
| <60 mg/dL (<3.3 mmol/L) or occurrence of 2 (or more) symptomatic hypoglycemic episodes or one severe hypoglycemic episode (requiring assistance) documented in the preceding week | - 2 to -4 or at the discretion of the Investigator or medically qualified designee |

Median refers to intermediate SMPG value (the value between the lowest and the highest SMPG values when the values are ranked in a growing order).

- **Attention for dose modification (iGlarLixi and IDegAsp):** iGlarLixi or IDegAsp dose titration may be withheld for a week or reduced in a participant who experiences two or more episodes of level 1 and/or level 2 hypoglycemia or one episode of level 3 hypoglycemia (requiring assistance from others to treat the hypoglycemic event)
- Participants who experienced hypoglycemia as a result of a missed meal, unusual exercise, or alcohol use will be counseled on the correction of those behaviors and may not need to have their insulin dose decreased.

- Investigators are allowed to modulate or stop titration or temporarily reduce dosage if they believe further titration would be hazardous to the participant (eg, due to age, comorbid conditions, individual participant considerations, other than hypoglycemia). In such a case the reason for the exceptions should be recorded in the source document.

Good clinical judgment is to be exercised in dose titration for investigators to identify any barriers for participants' titration compliance, eg., diet and exercise, alcohol consumption, and any concomitant illness. Participants should be familiarized with the titration schedule so that they would be able to monitor the titration with the assistance of the investigator or medically qualified designee. Investigators and qualified designees are encouraged to communicate with participants during the dose titration. More frequent contact via telecommunications eg, phone call, text message, WeChat etc can be added between visits if needed.

6.2 STUDY INTERVENTION PACKAGING AND LABELING

Packaging is in accordance with the administration schedule. The content of the labeling is in accordance with the local regulatory specifications and requirements.

The appropriate number of kits will be dispensed to cover up to the next dispensing visit (see the study flowchart in [Section 1.3](#)). Storage conditions and use-by-end date are part of the label text.

Treatment kit labels will indicate the treatment number (used for treatment allocation and reported in the eCRF). The participant number, visit number, and date of dispensation will be entered manually by the site staff on the treatment box label prior to dispensing.

In case of emergency only, for scheduled or unscheduled visits, the IMP might be supplied from the site to the participant via a Sponsor-approved courier company where allowed by local regulations. Direct-To-Patient (DTP) remains an option and the participant/investigator can refuse this option.

6.3 PREPARATION/HANDLING/STORAGE/ACCOUNTABILITY

The Investigator or designee must confirm appropriate temperature conditions have been maintained during transit for all study intervention received and any discrepancies are reported and resolved before use of the study intervention.

Only participants enrolled in the study may receive study intervention and only authorized site staff may supply or administer study intervention. All study intervention must be stored in a secure, environmentally controlled, and monitored (manual or automated) area in accordance with the labeled storage conditions with access limited to the Investigator and authorized site staff.

The Investigator, institution, or the head of the medical institution (where applicable) is responsible for study intervention accountability, reconciliation, and record maintenance (ie, receipt, reconciliation, and final disposition records).

Any quality issue noticed with the receipt or use of an IMP/NIMP/device (deficiency in condition, appearance, pertaining documentation, labeling, expiration date, etc.) must be promptly notified to

the Sponsor. Some deficiencies may be recorded through a complaint procedure (see [Section 8.3.8](#)).

A potential defect in the quality of IMP/NIMP/device may be subject to initiation of a recall procedure by the Sponsor. In this case, the Investigator will be responsible for promptly addressing any request made by the Sponsor, in order to recall the IMP/NIMP/device and eliminate potential hazards.

Under no circumstances will the Investigator supply IMP/NIMP/device to a third party (except for DTP shipment, for which a courier company has been approved by the Sponsor), allow the IMP/NIMP/device to be used other than as directed by this clinical trial protocol, or dispose of IMP/NIMP/device in any other manner.

6.4 MEASURES TO MINIMIZE BIAS: RANDOMIZATION AND BLINDING

- The randomized intervention kit number list is generated centrally by Sanofi.
- The IMPs are packaged in accordance with this list.
- An interactive response technology (IRT) will generate the participant randomization list and allocates the intervention number and the corresponding intervention kits to the participants according to it.
- All participants will be centrally assigned to randomized study intervention using an IRT. Before the study is initiated, the telephone number and call-in directions for the IVRS and/or the log in information and directions for the IWRS will be provided to each site.
- Study intervention will be dispensed at the study visits summarized in the SoA.
- Returned study intervention should not be re-dispensed to the participants.
- The randomization will be stratified by value of screening HbA1c (<8%, ≥8%), and by use at screening of metformin alone or metformin +SGLT2 (Yes/No).
- The overall objective of this last stratification group is to ensure that participants who will need to discontinue their second OAD are well balanced between groups. Definition of a randomized participant: a participant from screened population who has been allocated to a randomized intervention regardless of whether the intervention was received or not.
- A participant cannot be randomized more than once in the study.
- This is an open-label study because of the existing differences in the type and features of pens used to administer the iGlarLixi and IDegAsp. To compensate for the lack of blinding, the Investigator and the Sponsor will not have access to the data of the primary efficacy parameters (HbA1c, objectively collected and measured at a central laboratory) obtained after baseline visit until the end of the study.
However, the study team may review the data for the primary efficacy parameter in descriptive statistics with the name of the IMP treatment masked during data review meetings.

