8.1.1 HbA1c, FPG and fasting C-peptide measurement

For the eligibility and efficacy assessments of the study, HbA1c, FPG and fasting C-peptide are measured by a Chinese national certified central laboratory. Please refer to the flowchart in SoA.

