10.2 APPENDIX 2: CLINICAL LABORATORY TESTS

- The tests detailed in below [Table 8](#) will be performed by the central laboratory.
- Local laboratory results are only required in the event that the central laboratory results are not available in time for either study intervention administration and/or response evaluation. If a local sample is required, it is important that the sample for central analysis is obtained at the same time. Additionally, if the local laboratory results are used to make either a study intervention decision or response evaluation, the results must be recorded.
- Protocol-specific requirements for inclusion or exclusion of participants are detailed in [Section 10.5](#) of the protocol.
- Additional tests may be performed at any time during the study as determined necessary by the Investigator or required by local regulations [(for instance, when participants with known acquired immunodeficiency syndrome (AIDS)-related illness or known HIV disease requiring antiviral treatments need to be excluded, an HIV serology testing at screening is mandatory for German participants)].

Table 8 - Protocol-required laboratory tests

| Laboratory tests | Parameters |
|---------------------------------|--|
| Hematology | Platelet count Red blood cell (RBC) count Hemoglobin Hematocrit RBC indices: 
 • MCV • MCH • %Reticulocytes White blood cell (WBC) count with differential: 
 • Neutrophils • Lymphocytes • Monocytes • Eosinophils • Basophils |
| Clinical chemistry ^a | Blood urea nitrogen (BUN) Creatinine Glucose [Indicate if fasting, or nonfasting] Potassium Sodium Calcium Aspartate aminotransferase (AST)/ Serum glutamic-oxaloacetic transaminase (SGOT) Alanine aminotransferase (ALT)/ Serum glutamic-pyruvic transaminase (SGPT) Alkaline phosphatase ^b Total and direct bilirubin Total protein Amylase Lipase Calcitonin |
| Pregnancy testing | 
 • Urine human chorionic gonadotropin (hCG) pregnancy test (as needed for women of childbearing potential)^c |
| Other screening tests | 
 • Follicle-stimulating hormone and estradiol (as needed in women of non-childbearing potential only) • All study-required laboratory tests will be performed by a central laboratory |
| Other study specific tests | 
 • FPG, HbA1c, fasting C-peptide, SMPG |

| Laboratory tests | Parameters |

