A regional or national emergency declared by a governmental agency (eg, public health emergency, natural disaster, pandemic, terrorist attack) may prevent access to the clinical trial site.

Contingency procedures are suggested below and in sections for an emergency that prevents access to the study site, to ensure the safety of the participants, to consider continuity of the clinical study conduct, protect trial integrity, and assist in maintaining compliance with Good Clinical Practice in Conduct of Clinical Trials Guidance. Sponsor agreement **MUST** be obtained prior to the implementation of these procedures for the duration of the emergency.

During the emergency, if the site will be unable to adequately follow protocol mandated procedures, alternative treatment outside the clinical trial should be proposed, and screening/enrollment/randomization/administration of study intervention may be [temporarily delayed/halted].

Attempts should be made to perform all assessments in accordance with the approved protocol to the extent possible. In case this is not possible due to a temporary disruption caused by an emergency, focus should be given to assessments necessary to ensure the safety of participants and those important to preserving the main scientific value of the study.

Procedures to be considered in the event of a regional or national emergency declared by a governmental agency:

- If onsite visits are not possible, remote visits (eg, with home nurses, home health vendor, etc.) may be planned for the collection of possible safety and/or efficacy data.
- If onsite visits are not possible visit windows may be extended for assessment of safety and/or efficacy data that cannot be obtained remotely.
- Use of local clinic or laboratory locations may be allowed.

Informed consent: For a regional or national emergency declared by a governmental agency, contingency procedures may be implemented for the duration of the emergency. The participants or their legally authorized representative should be verbally informed prior to initiating any changes that are to be implemented for the duration of the emergency (eg. study visit delays/treatment extension, use of local labs).

- Contingencies implemented due to emergency will be documented.

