3.6.3 Additional safety assessments

3.6.3.1 Laboratory variables, vital signs and electrocardiograms (ECGs)

The following laboratory variables, vital signs and electrocardiogram (ECG) variables will be analyzed. They will be converted into standard international units.

- Hematology:
 - Red blood cells and platelets: hemoglobin, hematocrit, red blood cell count, platelet count, red blood cell indices (MCV, MCH, %Reticulocytes)
 - White blood cells: white blood cell count, neutrophils, lymphocytes, monocytes, basophils, eosinophils

- Clinical chemistry:
 - Metabolism: glucose, total protein, lipase, amylase
 - Electrolytes: sodium, potassium, calcium
 - Renal function: creatinine, creatinine clearance, eGFR, blood urea nitrogen, uric acid
 - Liver function: alanine aminotransferase, aspartate aminotransferase, alkaline phosphatase, gamma glutamyl transferase, total and direct bilirubin
 - Pregnancy test: urine human chorionic gonadotropin (hCG) (as needed for women of childbearing potential)
- Vital signs: heart rate, systolic and diastolic blood pressure in sitting position, and weight
- ECG variables: ECG assessments will be described as normal, abnormal and clinically significant (Y/N) if abnormal

Data below the lower limit of quantitation/detection limit (LLOQ) will be replaced by half of the LLOQ, data above the upper limit of quantification will be replaced by ULOQ value.

Quantitative analyses

When relevant, for laboratory variables and vital signs above, descriptive statistics for results and changes from baseline will be provided for each visit, the last value and the worst value (minimum and/or maximum value depending on the parameter) during the on-treatment period. These analyses will be performed using central measurements only (when available) for laboratory variables.

Analyses according to PCSA

Potentially clinically significant abnormality (PCSA) analyses will be performed based on the PCSA list currently in effect at Sanofi at the time of the database lock. For parameters for which no PCSA criteria are defined, similar analyses will be done using the normal range, if applicable. For parameters defined as efficacy endpoints, PCSA summaries will not be provided.

Analyses according to PCSA will be performed based on the worst value during the treatment-emergent period, using all measurements (either scheduled, nonscheduled or repeated).

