5.4 APPENDIX 4 DATA HANDLING CONVENTIONS

Analysis windows for HbA1c and body weight

The following analysis windows will be used to decide how the scheduled and/or unscheduled visits will be used in the analyses of efficacy variables: HbA1c and body weight.

A measurement (scheduled or unscheduled, central or local, pre-rescue and premature end of treatment) will be used if it is available and measurement date is within the analysis window.

After applying these time windows, if multiple assessments are associated to the same time point, the closest from the targeted study day will be used. If the difference is a tie, the value after the targeted study day will be used. If multiple valid values exist within a same day, then the first value of the day will be selected.

If there is no measurement for a given parameter in an analysis window, data will be considered missing for the corresponding visit.

The analysis window for HbA1c and body weight is given below.

Table 7 - Analyses window definition for HbA1c and body weight

Scheduled visit post baseline	Targeted study day	Analysis window in study days
Week 4 (Visit 6)	28	1 to 41
Week 8 (Visit 8)	56	42 to 69
Week 12 (Visit 10)	84	70 to 104
Week 18 (Visit 12)	126	105 to 146
Week 24 (Visit 14)	168	≥147

Study days are calculated considering Day 1 as the day of the first injection of open label IMP (or the day of randomization for participant not exposed).

Analysis windows for other endpoints

For safety parameters and efficacy parameters other than HbA1c and body weight, unscheduled, pre-rescue and premature end of treatment assessments will be reallocated to the closest scheduled visit per the schedule of assessment only if the scheduled assessment is missing with the rules defined below:

- Lower bound = targeted day of current scheduled visit - integer part of (targeted day of current scheduled visit – targeted day of the preceding scheduled visit)/2;
- Upper bound = targeted day of current scheduled visit + integer part of (targeted day of the next scheduled visit – targeted day of current scheduled visit -1)/2;
- Lower bound for the first scheduled post-baseline visit is always Day 1 (the day of first IMP injection);
- No upper bound is specified for the last scheduled post-baseline visit.

Unscheduled visits

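### SAP 5.4 lets local HbA1c into the primary analysis on equal terms with central HbA1c, at odds with Protocol 8.1.1 and the Section 6.4 open-label safeguard

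*Protocol*

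**What the plan says.** **The safeguard.** Protocol 6.4 explains why the trial is open-label and names the compensation: the Investigator and Sponsor "will not have access to the data of the primary efficacy parameters (HbA1c, objectively collected and measured at a central laboratory") obtained after baseline, until the end of the study. Protocol 8.1.1 agrees on the source: for eligibility and efficacy, "HbA1c, FPG and fasting C-peptide are measured by a Chinese national certified central laboratory". The schedule of activities (1.3) lists HbA1c under central laboratory tests, including at Visit 14 and at early discontinuation.

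**The analysis rule.** SAP 5.4 sets a windowing convention for two variables only, body weight and HbA1c. It reads: "A measurement (scheduled or unscheduled, central or local, pre-rescue and premature end of treatment) will be used if it is available", provided that its date falls in the window. If a window holds several values, the one closest to the target day is taken. A tie goes to the value after the target. Within a day, "If multiple valid values exist within a same day, then the first value of the day will be selected". The Week 24 window is Day 147 onward, with Day 168 as target.

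**Routes to a local value.** Protocol 10.2, whose Table 8 includes HbA1c, requires local results only when central ones are not available in time for administering the intervention or evaluating response. It adds: "If a local sample is required, it is important that the sample for central analysis is obtained at the same time". It also says: "Additional tests may be performed at any time during the study as determined necessary by the Investigator". Under the emergency contingency in Appendix 6 (10.6), "Use of local clinic or laboratory locations may be allowed".

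**For contrast.** For quantitative summaries of safety laboratory data, SAP 3.6.3.1 says: "These analyses will be performed using central measurements only (when available) for laboratory variables".

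**The concern.** The SAP rule does not carry through what the protocol says about the primary variable. Body weight is not a laboratory test, so in a convention covering only HbA1c and body weight, the words admitting local values can refer only to HbA1c. Laboratory source is not a criterion at any selection step.

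The rule fixes the Week 24 HbA1c for the non-inferiority test, for superiority test 2a and for responder endpoints 2c to 2e. It also supplies the Week 8, 12 and 18 values in the imputation model (SAP 3.2.2). If local values entered unevenly, the treatment difference could move. Neither sensitivity analysis in SAP 3.2.3 (the repeated-measures model and the penalized imputation) separates local from central values, and no count by source is planned. A reader of the results could not tell whether the central-measurement part of the safeguard had held.

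**Working it through.** **1. How the selection rule behaves.** Visit 14 may fall up to 4 days either side of schedule (1.3).

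- *Different days.* Suppose the central Visit 14 sample is drawn on Day 172 and a local HbA1c is recorded on Day 167. The distances from Day 168 are 4 and 1. SAP 5.4 selects the local value although a central one exists.
- *Same time.* Protocol 10.2 asks for a central sample alongside any local one. Both have the same distance from target and the same date. The within-day rule takes the first, but neither sample is first when they are drawn together.

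**2. The plan's own sample size.** Inputs from Protocol 9.1 and SAP 4: margin 0.3, SD 1.05, true difference 0, one-sided 0.025 (two-sided 0.05), power 90%, dropout 10%.

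- Normal approximation: n = 2 × 1.05² × (1.960 + 1.282)² / 0.3² = 257.4, so 258 per arm. 258/0.9 = 286.7, so 287 per arm, 574 in total.
- Two-sample t-test: 259 per arm. 259/0.9 = 287.8, so 288 per arm, 576 in total.

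The stated 580 is consistent with both. Nothing below changes it.

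**3. Room below the margin at the planned size.**

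- Evaluable per arm: 290 × 0.9 = 261.
- SE = 1.05 × √(2/261) = 0.0919.
- 95% half-width = 1.9645 × 0.0919 = 0.1806 (t, 520 df).
- Non-inferiority needs a point estimate below 0.3 − 0.1806 = 0.1194.

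**4. What a local value can do.** Let p be the share of Week 24 values that are local in an arm, and b the mean local-minus-central offset in that arm. The treatment difference shifts by

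p(iGlarLixi) × b(iGlarLixi) − p(IDegAsp) × b(IDegAsp).

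This is zero when p and b are the same in both arms. With a common offset b it reduces to the net excess share times b.

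**5. Illustration.** The documents give neither p nor b. The assumed ranges are a net excess of 1% to 10% in one arm and an offset of 0.1 to 0.5 points. The error column is the one-sided error at a true difference of 0.3 if the shift favours iGlarLixi. The power column applies at a true difference of 0 if the shift goes against it. Both use the noncentral t with 520 df.

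| Net excess × offset | Shift | Share of 0.1194 | One-sided error | Power |
|---|---|---|---|---|
| none | 0 | 0% | 2.5% | 90.3% |
| 1% × 0.1 | 0.001 | 0.8% | 2.6% | 90.1% |
| 2% × 0.5 | 0.01 | 8.4% | 3.2% | 88.3% |
| 10% × 0.3 | 0.03 | 25.1% | 5.1% | 83.5% |
| 10% × 0.5 | 0.05 | 41.9% | 7.8% | 77.5% |

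**The case against.** The strongest reply is that a local Week 24 HbA1c should hardly ever occur. All scheduled HbA1c is central. Titration runs on fasting SMPG, and the rescue retest in Protocol 6.8.4 is central. Protocol 10.2 requires local results only when central ones are late, and at Visit 14 treatment ends, so little is left to prompt one. The Appendix 6 route needs a declared emergency and Sponsor agreement. Additional tests are permitted, but no text says that they all reach the efficacy data. This stands: it limits how often the rule would matter, but it does not supply a rule for when it does.

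A second reply is that knowing the arm does not alter an assay, and that a site unable to see the central value cannot pick the better of two results. This also stands. A reader might infer that arm-aware sites can see and steer the primary endpoint, so that the open-label safeguard fails. The documents do not support that. No sentence says who sees local HbA1c. Visibility is a reasonable inference from Protocol 10.2, which lets local results inform site decisions, but nothing points to selective testing or recording. Nor does the Protocol 6.8.4 alert for HbA1c above 8% bear on this point: it is a disclosed rescue safeguard and lets no local value into the analysis.

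The safety-laboratory contrast concerns different analyses. It shows only that the SAP states a central preference elsewhere.

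**Conclusion.** The inconsistency holds on the current text. Protocol 6.4 and 8.1.1 rest on centrally measured HbA1c; SAP 5.4 treats a local value as its equal for the primary endpoint, can prefer it to an available central value, and leaves a simultaneous pair unresolved.

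Its size is unknown. The illustrative shift runs from 0.001 to 0.05 points, and every entry rests on an assumed imbalance between arms and an assumed offset. A reader might take the 7.8% in the table as the trial's type I error. It is not: it is the corner where both assumptions are at their largest and the direction favours iGlarLixi. With equal use and equal offset the shift is zero, and the documents suggest no imbalance.

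The change is still worth making, because the rule governs the primary endpoint, no planned analysis would reveal a problem, and the correction costs almost nothing.

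**What to change.** In SAP 5.4, for HbA1c:

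- When central and local values belong to the same visit (same day, or within that visit's protocol window, for example ±4 days for Visit 14), use the central value.
- Use a local value only if that visit has no central value.
- Do not let a central pre-rescue or early-discontinuation value displace a later local value from the scheduled Week 24 visit.

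The last clause is needed because the Week 24 window opens at Day 147, has no upper limit, and admits pre-rescue and premature end-of-treatment samples. If central values took priority anywhere in the window, a central sample at Day 148, taken before rescue, could replace a local Day 168 value taken after it. That would work against the treatment-policy estimand.

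Add one sensitivity analysis that sets local-only Week 24 values to missing and imputes them with the planned multiple imputation. Report the number of local Week 24 values by arm.

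No change is needed to Protocol 6.4, Appendix 6 or the Protocol 6.8.4 alert. The cost is one SAP rule and one extra analysis run. Visits, samples, margin and sample size stay as they are.
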